## SCHEMA

### **Treatment Plan:**

#### **Pre-treatment Period**

Screening assessments will be performed as described below:

Days -21 to -1: (within 21 days prior to start of treatment). Informed consent; medical history; physical exam (PE) with vital signs, including height and weight; ECOG performance status and review of concomitant medications and electrocardiogram (EKG) will be ordered. Tumor tissue from a previous paraffin block will be obtained for correlative studies.

Days -14 to -1: (within 14 days of start of treatment). PE with vital signs and weight; review of any new events in medical history and medication; ECOG performance status will be repeated. Assessment and tumor imaging (CT scans and optional PET/CT scans) will also be obtained.

Day -7 to day 1 prior to study drug start: Hematology, comprehensive metabolic chemistry profile, coagulation profile and urinalysis will be obtained. Women of childbearing potential will have a serum pregnancy test done.

#### **Treatment Period:**

Vorinostat will be administered orally once daily continuously at 400 mg. Each treatment cycle will consist of 4 weeks of daily treatment.

Study visits will be conducted on weeks 2 and 4 ( $\pm 1$  day) for the first cycle, then for the second cycle on week 5 and 7, ( $\pm 1$  day); then from week 9 on, every four weeks ( $\pm 1$  day) thereafter for the remainder of the study. Patient medical histories, physical examinations, laboratory tests, assessments of compliance with study medication and recording of adverse events will be conducted during study visits. Further blood may be drawn for research correlatives. For patients that have been on study longer than 2 years, office visits can be done every 12 weeks ( $\pm 7$  days), with medical history, concurrent meds, physical exam, vital signs, weight, performance status, and adverse events evaluation done also at that time. For patients that have been on study longer than 2 years, hematology labs and serum chemistry can be done every 6 weeks ( $\pm 7$  days).

The severity duration and relationship to vorinostat will be determined for each adverse experience (AE) ([Section 11](#)).

Blood will be drawn on days 1 prior to first drug intake, and on days 7 (+- 1 day) and 28 (+- 1 day), prior to drug intake, to assess for correlative studies.

Patients will have radiological tumor assessment by computed tomography (CT) scan (or magnetic resonance imaging - MRI) on days -14 to -1 (prior to the start of vorinostat) and day 56 ( $\pm 3$  days). They will be followed with CT scans or MRI every 2 cycles / 8 weeks ( $\pm 1$  week) thereafter. Patients may receive scans every 3 cycles/12 weeks ( $\pm 1$  week) after completing 6 months of treatment on study. Patients that have been on study longer than 2 years can have tumor measurements (CT scans or MRI) done every 24 weeks ( $\pm 10$  days).

Predicated on obtaining funding, additional scans (optional) will be performed. These will include PET/CT scans prior to treatment, Day 28 ( $\pm 3$  days), and Day 56 ( $\pm 3$  days). An additional CT scan or MRI will also be performed on Day 28 ( $\pm 3$  days) for comparison purposes. The Day 28 CT/MRI and the PET/CT scans will be optional studies- due to financial issues (funding).

Vorinostat will be withheld for any possible or probable drug related grade 3 to 4 adverse event. Patients will be allowed to have 2 dose reductions (from 300mg/day D1-7 to 300mg/day D1-5) due to grade 3 nausea, emesis or diarrhea (not controlled by appropriate supportive care measures); due to other drug-related grade 3/4 non-hematological toxicity; due to grade 3/4 neutropenia associated with fever and/or grade 4 neutropenia and/or grade 4 thrombocytopenia ([section 6](#)). In the event a patient is experiencing clinical benefit from vorinostat and requires further dose reduction, a discussion between CTEP and PI will ensue.

Patients who cannot be retreated within 3 weeks (21 days) of the end of the previous cycle should be removed from study, unless they are deriving benefit. In the later case, a discussion with the PI and/or CTEP senior investigator will also ensue.

Patients who experience either stable disease, complete response, or partial response by RECIST criteria will be allowed to continue on vorinostat as long as they are experiencing benefits without intolerable/life-threatening side effects.

#### **Post-treatment Period:**

Patients with progression of disease (PD), unacceptable toxicity, or uncontrolled intercurrent illness will be taken off the trial. Other criteria for discontinuation will include: patient withdrawal of consent, noncompliance with study medication or visits, or any change that would render the patient ineligible for further treatment. In those cases, patients will be entered on the post-treatment period. The end of study visit should occur within 30 days of the last dose of the study drug. Patient medical histories, physical examinations and laboratory tests will be obtained. Tumor imaging if not done in the last 30 days, will be ordered at this time. The investigator or designee will obtain follow-up information on the patient at 180 days after the last dose of the study drug or until death (if before 180 days).

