### **5.4 Duration of Follow Up**

Patients will be followed for 180 days after removal from study or until death, whichever occurs first. Patients removed from study for unacceptable adverse events will be followed until resolution or stabilization of the adverse event.

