| Height  | X b             |  |                |      |                |                |      |                |      |                |          |                |                |
| Weight n                           | X b,c           |  | X e |      | X e | X e |      | X e |      | X e |          | X e | X              |
| Performance status (ECOG) n        | X b,c           |  | X e |      | X e | X e |      | X e |      | X e |          | X e | X              |
| Hematology labs d,o                | X c             |  | X e |      | X e | X e |      | X e |      | X e |          | X e | X              |
| Serum chemistry f,o                | X c             |  | X e |      | X e | X e |      | X e |      | X e |          | X e | X              |
| EKG   | X b             |  |                |      |                |                |      |                |      |                |          |                |                |
| Urinalysis                                    | X c             |  |                |      |                |                |      |                |      |                |          |                |                |
| B-HCG g                            | X c             |  |                |      |                |                |      |                |      |                |          |                |                |
| Adverse events evaluation n        |                            |  | X e |      | X e | X e |      | X e |      | X e |          | X e | X              |

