#### 11.1.1 Expedited Reporting Guidelines – Phase 2 studies with investigational agents (including hospitalization defined in bullet 1 below)

#### CTEP-AERS Reporting Requirements for Adverse Events that occur within 30 Days of the Last Dose of the Investigational Agent on Phase 2 and 3 Trials

| Phase 2 and 3 Trials  |                         |                  |              |                                 |                         |                               |                         |                           |                           |
|---|-------------------------|------------------|--------------|---------------------------------|-------------------------|-------------------------------|-------------------------|---------------------------|---------------------------|
|   | Grade 1                 | Grade 2          | Grade 2      | Grade 3                         |                         | Grade 3                       |                         | Grades 4 & 5  | Grades 4 & 5  |
|   | Unexpected and Expected | Unexpected       | Expected     | Unexpected with Hospitalization | without Hospitalization | Expected with Hospitalization | without Hospitalization | Unexpected                | Expected                  |
| Unrelated Unlikely   | Not Required            | Not Required     | Not Required | 10 Calendar Days                | Not Required            | 10 Calendar Days              | Not Required            | 10 Calendar Days          | 10 Calendar Days          |
| Possible Probable Definite   | Not Required            | 10 Calendar Days | Not Required | 10 Calendar Days                | 10 Calendar Days        | 10 Calendar Days              | Not Required            | 24-Hour; 5 Calendar Days  | 10 Calendar Days          |

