|  Adverse events with attribution of possible, probable, or definite that occur greater than 30 days after the last dose of treatment with an agent under a CTEP IND require reporting as follows:
CTEP-AERS 24-hour notification followed by complete report within 5 calendar days for: 
 
Grade 4 and Grade 5 unexpected events
 
 CTEP-AERS 10 calendar day report: 
 
Grade 3 unexpected events with hospitalization or prolongation of hospitalization
 
Grade 5 expected events
 
  Although an CTEP-AERS 24-hour notification is not required for death clearly related to progressive disease, a full report is required as outlined in the table. |                         |                  |              |                                 |                         |                               |                         |                           |                           |
| December 15, 2004   |                         |                  |              |                                 |                         |                               |                         |                           |                           |

***Note: All deaths on study require both routine and expedited reporting regardless of causality. Attribution to treatment or other cause must be provided.***

- Expedited AE reporting timelines defined:
  - “24 hours; 5 calendar days” – The investigator must initially report the AE via CTEP-AERS within 24 hours of learning of the event followed by a complete CTEP-AERS report within 5 calendar days of the initial 24-hour report.
  - “10 calendar days” - A complete CTEP-AERS report on the AE must be submitted within 10 calendar days of the investigator learning of the event.
- Any medical event equivalent to CTCAE grade 3, 4, or 5 that precipitates hospitalization (or prolongation of existing hospitalization) must be reported regardless of attribution and designation as expected or unexpected with the exception of any events identified as protocol-specific expedited adverse event reporting exclusions.
- Any event that results in persistent or significant disabilities/incapacities, congenital anomalies, or birth defects must be reported via CTEP-AERS if the event occurs following treatment with an agent under a CTEP IND.

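### The last scheduled adverse-event evaluation may fall on any day up to day 30 after the last dose, and no contact closes the 30-day reporting window

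*Combined protocol and SAP*

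**What the plan says.** **Visit timing.** The Schema, under Post-treatment Period, states: "The end of study visit should occur within 30 days of the last dose of the study drug". It sets no earliest day and no target day.

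**Where adverse events are collected.** Under Treatment Period, the Schema says that "recording of adverse events will be conducted during study visits". For the end-of-study visit it says "Patient medical histories, physical examinations and laboratory tests will be obtained" and does not name adverse events. The Section 9 calendar fills that gap: the row "Adverse events evaluation" has its last mark in the Off Study column. Nothing later is scheduled.

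**Reporting window.** The table in Section 11.1.1 is headed "CTEP-AERS Reporting Requirements for Adverse Events that occur within 30 Days" of the last dose. Its first footnote keeps a narrower duty after that. Events with possible, probable or definite attribution that occur more "than 30 days after the last dose of treatment with an agent under a CTEP IND require reporting as follows", and a shorter list follows. Both reporting timelines run from the investigator learning of the event.

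**Later follow-up.** The Schema says that the site "will obtain follow-up information on the patient at 180 days after the last dose of the study drug"; an earlier death ends this follow-up. Section 5.4 instead follows every patient for 180 days counted from removal from study, or until death. Neither gives a contact schedule or says that adverse events will be asked about. Section 5.4 adds: "Patients removed from study for unacceptable adverse events will be followed until resolution or stabilization of the adverse event".

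**Analysis.** Section 12.4 reports toxicity proportions with 90% Wilson intervals. Section 12.5.1 starts the toxicity period at first treatment and gives no end.

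**The concern.** The window in which events must be reported is fixed at 30 days for everyone. The planned collection of those events stops on whichever day the off-study visit happens to be held. Two patients followed exactly to plan can therefore have post-treatment ascertainment that differs by up to about 30 days, for reasons unrelated to toxicity.

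Two things are at stake. The first is safety reporting. A duty triggered by knowledge needs a contact that produces the knowledge, and the in-window duty is broad. Under Section 11.1.1, grade 3 events with hospitalization and all grade 4-5 events are reportable within 30 days even when judged unrelated or unlikely to be related. After day 30 the footnote covers only events attributed to the drug. The second is Secondary Objective 1. An event that is never learned of can only lower a toxicity proportion, and a single-arm trial has no comparator to show that this has happened.

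A related gap concerns events still open at the visit. Follow-up to resolution or stabilization is explicitly required only when the adverse event was the reason for removal. A patient who leaves for progression with the same unresolved drug-related grade 3-4 event is not covered by that clause.

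**Working it through.** The plan gives no figure to reproduce here, so the check compares the rules and then does day arithmetic.

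**Inputs from the plan**
- Latest permitted visit: day 30 after the last dose (Schema, Post-treatment Period). Earliest day: none stated.
- Last scheduled adverse-event evaluation: Off Study column (Section 9).
- Full expedited-reporting window: 30 days after the last dose (Section 11.1.1).
- Next dated follow-up: day 180 after the last dose (Schema).

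**Assumed:** the visit day *d*. The plan gives no distribution, so a range is shown.

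**Formulas:** days of the window after the visit = 30 − *d*; share = (30 − *d*)/30; interval to the Schema's dated follow-up = 180 − *d*.

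| Visit day *d* (assumed) | 30 − *d* | Share of window | 180 − *d* |
|---|---|---|---|
| 7 | 23 | 77% | 173 |
| 14 | 16 | 53% | 166 |
| 21 | 9 | 30% | 159 |
| 28 | 2 | 7% | 152 |
| 30 | 0 | 0% | 150 |

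The shares count calendar days, not events. They show how much of the window lacks planned ascertainment and do not estimate bias.

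**What one missed patient does to a rate.** At the sample sizes Section 12.4 uses, one patient is 1/12 = 8.3 percentage points at Stage 1 and 1/29 = 3.4 points at Stage 2. The 12 and 29 are response-evaluable counts (Section 12.1.1). The toxicity denominator is every treated patient (Sections 10.1.1 and 12.5.1), which is at least as large, so with each stage fully accrued these are upper limits per missed patient.

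**The two follow-up statements**

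| | Schema, Post-treatment Period | Section 5.4 |
|---|---|---|
| Clock starts | Last dose | Removal from study |
| Form | Information obtained at day 180 | Followed for 180 days |
| Contact schedule | None beyond day 180 | None |
| Adverse-event content | Not stated | Only for patients removed for unacceptable adverse events |

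Neither supplies a contact at or near day 30.

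**Design.** The primary endpoint is response. With at least 1 of 12 needed to continue and at least 3 of 29 to call the drug promising, exact binomial calculation gives early termination probability 0.540 and alpha 0.148 at a 5% response rate, and power 0.9005 at 20%. These agree with the stated 0.540, 0.15 and 0.90. None depends on adverse-event ascertainment.

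**The case against.** The strongest case on the other side has four parts.

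*Follow-up does not stop at the visit.* A reader might infer from the Schema that nothing happens between the off-study visit and one contact at day 180. The documents do not support that: Section 5.4 keeps every patient under follow-up for 180 days after removal. A reader might also infer that a patient who leaves for progression with ongoing toxicity gets no follow-up at all. That goes too far as well, because the same sentence covers that patient and the Schema asks for the duration of each adverse event to be determined. What remains is that this follow-up has no schedule and no stated adverse-event content. For the same reason it cannot be said that events are picked up at day 180, since questioning about them then is not shown.

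*A reporting rule is not a solicitation window.* This is correct. Section 11 says what must be reported, not how often patients must be asked, and the duty continues in narrower form after day 30. The gap is in active ascertainment. Deaths are the least likely to be missed, because patients are followed to death within the 180 days and overall survival is an endpoint.

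*The effect may be small.* Section 2.2 says most dose-limiting toxicities occurred within the first month on oral drug and resolved quickly after interruption, and it gives an oral half-life of 92 to 150 minutes. This supports a modest effect on drug-related rates. It does not close the gap, because much of the in-window duty applies whatever the attribution.

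*The timing is unknown.* It is tempting to picture the off-study visit in the same week as a progression scan, with most patients leaving for progression. The documents give no source for either, and they equally permit visits on days 21 to 30, when the gap is small or absent.

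**Conclusion.** The point holds as a gap in planned ascertainment. A site can follow the plan exactly and leave from 0 to about 30 of the 30 reportable days without a scheduled adverse-event contact, depending only on the visit date: 23, 16, 9 or 2 days for visits on days 7, 14, 21 or 28, and none for day 30. These visit days are assumed.

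Events in the uncovered days remain reportable but may be learned late or missed. Measured against toxicity through day 30, the rates in treated patients can only be lowered. The documents do not allow the amount to be estimated, and Section 2.2 suggests it is modest. Taking day 30 as the target is itself an assumption, because Section 12.5.1 names no end. The consequence is confined to safety reporting and the descriptive results of Secondary Objective 1. This is an inexpensive improvement to the plan and does not threaten the efficacy conclusion.

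**What to change.** 1. In the Schema's Post-treatment Period and the calendar's Off Study column, add an adverse-event contact at day 30 after the last dose (for example, with a window of +7 days). It can be by telephone when the off-study visit came earlier.
2. In Section 12.5.1, state that the adverse-event period for the toxicity rates runs from first treatment through day 30 after the last dose.
3. In Section 5.4, apply follow-up to resolution or stabilization to any drug-related grade 3-4 event unresolved at the off-study visit, whatever the reason for removal.
4. Reconcile the 180-day statements in the Schema and Section 5.4: one starting point, a stated form of contact, and whether adverse events are asked about.

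The cost is about one call for each patient whose visit falls before day 30, continued follow-up of the few events still open, and the wording changes. Reported toxicity rates may come out slightly higher. No dose or treatment rule changes.

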#### **Correlative Studies:**

The correlative portion of this trial is described the Laboratory Correlates section ([appendix D](#)). In a retrospective pilot study, CT and or MRI scans already obtained from all the patients in the trial will be re-reviewed. RECIST imaging will be compared to volumetric density (viable tumor volume VTV) CT and MR measurements. The objective is to establish whether volumetric density/percent necrosis algorithms such as VTV more accurately assess the extent of the disease and response to therapy than standard RECIST criteria.

## **1. OBJECTIVES**

### **1.1. Primary Objectives**

- To evaluate the efficacy by means of response rate (based on RECIST 1.1 criteria) of vorinostat in the treatment of patients with locally advanced, recurrent or metastatic adenoid cystic carcinoma (ACC).

### **1.2 Secondary Objectives**

- To characterize the safety and tolerability of vorinostat in this patient population.
- To assess the time to tumor response (TTR).
- To assess the response duration (RD).
- To evaluate progression free survival (PFS).
- To assess overall survival (OS).

### **1.3 Exploratory Objectives**

- To assess the association between a metabolic response by PET/CT after one cycle of chemotherapy and subsequent best tumor response according to standard anatomic response evaluation criteria (RECIST).
- To assess the association between a metabolic response by PET/CT after the first and second chemotherapy cycle and PFS.
- Flow sort diploid, aneuploid, and tetraploid populations of tumor cells from FFPE tissue blocks from patients who benefited from SAHA therapy and from patients who did not demonstrate a durable benefit.
- Profile the genomes of each cell population using oligonucleotide CGH arrays. This will confirm the identification of tumor populations in each sample and provide genomic landmarks for NGS analysis.
- Perform whole exome analysis of the sorted tumor population and matching germ line sample for each of the patients selected
- To assess stable disease duration (SDD)
- To assess the association between response to vorinostat treatment and HR23B on tumor paraffin blocks
- Retrospectively compare volumetric density (viable tumor volume=VTV) with pre-determined RECIST of target lesions in cross sectioning imaging (CT/MR) already obtained
- Correlate VTV, RECIST and treatment response (partial response, stable disease, progressive disease and stable disease over 6 months)

## **2. BACKGROUND**

### **2.1 Adenoid Cystic Carcinoma**

Tumors of the salivary gland comprise 3 to 6% of all head and neck neoplasms in adults; the

incidence is one to three per 100,000 people per year (1). Of the several types of salivary gland cancer, adenoid cystic carcinoma is the second most common type, accounting for 22% of cases in some series (2). ACC is an indolent cancer with 5-year survival rates as high as 50-90% and up to 25% 15-year survival rates. Surgery with wide resection is the main modality of treatment for localized ACC. Adjuvant radiation therapy is reserved for patients with poor prognostic factors, such as close or positive margins, vascular or perineural invasion, lymph node metastasis or high grade tumors. Loco-regional recurrence and distant metastasis especially to the lung are not uncommon. A watch and wait approach is appropriate if a patient has metastasis but has few or no symptoms due to the indolent nature of the tumor.

Response to chemotherapy agents is around 20% with single agents and 50% with combination therapy (3-10). There is no evidence that combination therapy is better than single agents and it is unknown if survival is improved with chemotherapy. Active single agents include cisplatin, 5-FU, doxorubicin, mitoxantrone and vinorelbine. New agents have also been studied, but so far their use remains investigational. In the largest study utilizing imatinib in patients with ACC that overexpressed c-kit, no partial or complete responses were seen, stable disease was achieved in 9 patients, some of them over 12 months (11). In a phase 2 study of trastuzumab in salivary gland tumors that overexpressed Her-2, a partial response was seen in 1 out of 14 patients (12). Another phase 2 trial utilizing lapatinib, a pan-Erb inhibitor (EGFR and HER-2) showed promising activity with 79% of ACC patients with stable disease, 47% of more than 6 months (13). A phase 2 trial of gefitinib showed no responses but stable disease in 68% of the patients (14). The use of cetuximab also showed no response, but stable disease in 50% of the patients with salivary gland tumors (15). A combination trial investigated the use of bortezomib and doxorubicin. Bortezomib was given until progression in patients with metastatic ACC. Doxorubicin was added at time of progression. There were no responses to single agent bortezomib, however, 64% of patients had stable disease (16).

Stable disease duration has been described in several trials (11,13,15,17,18) as so far partial or complete responses have been rarely obtained with the current regimens or experimental therapies. It is unclear if stable disease duration represents a marker of drug activity or only the indolent nature of this tumor. However, most phase II studies report stable disease duration for 6 months or more as an endpoint, therefore, especially in view of tumors that were progressing prior to study entry, this may be a relevant exploratory endpoint.

There is no established standard chemotherapy for the treatment of ACC. Therefore there is a need to perform high quality clinical trials in this setting. Multicenter cooperative trials should be included in order to maximize patient's resources due to the rarity of this cancer.

